14.3.2 During and Within 15 Minutes Post-End Transfusion

1. Begin RBC transfusion per site standard procedures

Note: As per the AABB Technical Manual, the initial flow rate for RBC transfusions should be 1-2 mL/min (60-120 mL/hr) for the first 15 minutes, with the total infusion duration \leq 4 hours⁴¹

2. Record start/end date/time(s) of transfusion(s)
3. Record volume of RBCs transfused
4. Record vital signs (HR, BP, RR, SpO₂, temperature) during transfusion at 15 (\pm 5) minutes after starting transfusion and hourly, at end of transfusion, and 15 (\pm 5) minutes after end of transfusion. A \pm 15 minute window is allowed unless otherwise specified
5. Collect blood for Local Laboratory Tests at 15 (+ 5) minutes post-end transfusion
 - a. CBC, plasma free hemoglobin and haptoglobin (Section 16.2.1)
 - b. Serum potassium and sodium concentrations
6. Record concomitant medications and all blood products transfused (eg, off-protocol RBCs, platelets) (Section 17)
7. Record AEs, SAEs, and UADEs (Section 19)

14.3.3 1 Day (24 \pm 6 hours) Post-Transfusion

1. Record vital signs (HR, BP, RR, SpO₂, temperature)
2. Collect blood for Local Laboratory Tests
 - a. CBC, plasma free hemoglobin and haptoglobin (Section 16.2.1)
 - b. Chemistry (Section 16.2.1)
3. Record concomitant medications and all blood products transfused (eg, off-protocol RBCs, platelets) (Section 17)
4. Record AEs, SAEs, and UADEs (Section 19)

14.3.4 7 Days (\pm 1 day) Post-Transfusion

1. Collect blood for Local Laboratory Tests
 - a. CBC and haptoglobin (Section 16.2.1)
 - b. Chemistry (Section 16.2.1)
 - c. RBC antibody screen
 - o If positive, conduct RBC antibody identification and record only new RBC antibodies, if applicable
 - d. Crossmatch with Mirasol-treated RBCs if the previous study transfusion was a MIR RBC product
2. Collect blood for Central Laboratory Tests (Section 16.2.2)
 - a. Collect and hold blood sample for central RBC antibody testing, when the antibody screen and crossmatch performed at the local lab either is positive for an antibody

specific to MIR-treated RBCs or inconclusive. See Section 16.2.2.1 for details regarding criteria for sending samples to the central laboratory

3. Record concomitant medications and all blood products transfused (eg, off-protocol RBC, platelets) (Section 17)
4. Record AEs, SAEs, and UADEs (Section 19)

14.4 End of Study Treatment Follow-up/Early Termination

All enrolled subjects who received at least 1 post-randomization RBC transfusion will complete a follow-up visit approximately 2-4 weeks after the last per protocol transfusion episode, prior to the next transfusion performed as standard of care.

In the event that a subject withdraws consent for study participation, an early termination visit should be scheduled as close as possible to the time when consent was withdrawn.

The following procedures will be completed for the follow-up visit and/or the early termination visit:

1. Conduct physical examination
 - a. Perform an abbreviated physical examination, including examination of general appearance, eyes/ears/nose/throat, pulmonary/chest, cardiovascular, abdominal, and neurological
2. Collect blood for Local Laboratory Tests (Section 16.2.1)
 - a. CBC, plasma free hemoglobin (only if subject is terminating within 24 hours after previous study transfusion) and haptoglobin
 - b. Chemistry
 - c. RBC antibody screen
 - o If positive, conduct RBC antibody identification and record only new RBC antibodies, if applicable
 - d. Crossmatch with Mirasol-treated RBCs if the previous study transfusion was a MIR RBC product
3. Collect blood for Central Laboratory Tests (Section 16.2.2)
 - a. Collect and hold blood sample for central RBC antibody testing, if applicable. See Section 16.2.2.1 for details regarding criteria for sending samples to the central laboratory
 - b. Collect blood sample for HLA testing, only if subject terminated from the study during Treatment Period 1 (Section 16.2.2.2)
4. Record concomitant medications and all blood products transfused (eg, off-protocol RBCs, platelets) (Section 17)

5. Record AEs, SAEs, and UADEs (Section 19)

14.5 Final Study Follow-up

All enrolled subjects will complete a final study follow-up visit, which can be concurrent with routine standard of care, at least 60 days after the last per protocol study transfusion episode.

1. Collect blood for Local Laboratory Tests (Section 16.2.1)
 - a. RBC antibody screen
 - b. If positive, conduct RBC antibody identification and record only new RBC antibodies, if applicable
2. Collect blood for Central Laboratory Tests (Section 16.2.2)
 - a. Collect and hold blood sample for central RBC antibody testing, if applicable. See Section 16.2.2.1 for details regarding criteria for sending samples to the central laboratory
3. Record AEs, SAEs, and UADEs (Section 19)

Table 14-1: Schedule of Procedures for Subjects

	Screening	With Each RBC Transfusion				End of Study Treatment Follow-up/ Early Termination	Final Study Follow-up
	(Days -28 to 0)	Prior to Transfusion	During and Within 15 min Post-Transfusion	1 Day (24 ± 6 hrs) Post-Transfusion ^p	7 Days (± 1 day) Post-Transfusion ^p		≥ 60 days after last transfusion
ICF/assent, ^a and Eligibility	X						
Demographics	X						
Medical/surgical history ^b	X						
Height and weight	X	X ^c					
Randomization	X ^d						
Identify target post-transfusion (15 min) Hb	X						
Record RBC details ^e			X				
Begin transfusion			X ^f				
Calculate the volume of RBCs required to achieve the target Hb		X					
Physical examination ^g	X	X				X	
Vital signs	X	X ^h	X ^h	X			
Routine blood typing and crossmatch, per site standard practice		X					
CBC, plasma free hemoglobin and haptoglobin ⁱ		X	X	X	X	X	
Chemistry		X	Serum K and Na only ^j	X	X	X	
Serum/urine pregnancy test ^k	X	X ^k					
RBC antibody screen and identification ^l		X			X	X	X
Crossmatch with Mirasol-treated RBCs ^m		X			X	X	

	Screening	With Each RBC Transfusion				End of Study Treatment Follow-up/ Early Termination	Final Study Follow-up
	(Days -28 to 0)	Prior to Transfusion	During and Within 15 min Post-Transfusion	1 Day (24 ± 6 hrs) Post-Transfusion ^b	7 Days (± 1 day) Post-Transfusion ^b	2-4 weeks after last transfusion	≥ 60 days after last transfusion
Central RBC antibody screen ⁿ		X			X	X	X
Central HLA antibody screen ^o		X				X	
Central supernatant K, Na and hemoglobin from RBC product		X					
Record concomitant medications		X	X	X	X	X	
Record all blood products, RBC details		X	X	X	X	X	
Record AEs, SAEs, and UADEs		X	X	X	X	X	X

Abbreviations: AE = adverse event, BP = blood pressure, CBC = complete blood count, HR = heart rate, ICF = informed consent form, K = potassium, Na = sodium, RBC = red blood cell, RR = respiratory rate, SAE = serious adverse event, SpO₂ = arterial oxygen saturation via pulse oximetry, UADE = unanticipated adverse device effect.

^a The ICF/parental consent/assent process may take place prior to the 28-day screening window.

^b Medical/surgical history should include thalassemia diagnosis information (ie, genotype [if available], phenotype, history of antibody formation [list of antibodies] and date of diagnosis); transfusion history (date of transfusion initiation, history of transfusion reactions in the previous 6 months [type, date], mean transfusion interval for the prior 6 months); and splenectomy status, immunizations, infection exposures in the 3 months prior to the screening visit, current organ dysfunction.

^c Height will be measured once at the screening visit. Weight will be measured prior to each transfusion.

^d If screening procedures confirm eligibility, the subject will be randomized within 10 days prior to initiation of the first study transfusion (Study Day 0).

^e Document RBC product details for each unit transfused per Section 13.3.

^f As per the AABB Technical Manual, the initial flow rate for RBC transfusions should be 1-2 mL/min (60-120 mL/hr) for the first 15 minutes, with the total infusion duration ≤ 4 hours.⁴¹

^g A full physical exam will be conducted at the screening visit and will include examination of general appearance, skin, eyes/ears/nose/throat, head/neck, pulmonary, chest, cardiovascular, abdominal and liver/spleen, lymphatic, musculoskeletal, and neurological. Abbreviated physical exams will be conducted prior to the first transfusion of Treatment Period 2 and at the Final Follow-up Visit, and will include examination of general appearance, eyes/ears/nose/throat, pulmonary/chest, cardiovascular, abdominal, and neurological.

^h Vital sign measurements will include HR, BP, RR, SpO₂, and temperature. On the days of transfusion, vital sign measurements will be obtained within 1 hour prior to transfusion, during transfusion at 15 (± 5) minutes and hourly, at end of transfusion, and 15 (± 5) minutes after end of transfusion. All vital sign measurements should be collected within ± 15 minutes of the nominal time point unless otherwise specified.

ⁱ A blood sample for the CBC, plasma free hemoglobin, and haptoglobin tests will be collected from the subject within 1 hour prior to transfusion, within 15 (\pm 5) minutes post-transfusion, and on Day 1 after each transfusion. In addition, on Day 7 (\pm 1 day) after each transfusion, a blood sample for CBC and haptoglobin tests will be collected.

^j Serum potassium and sodium from the subject within 15 (+ 5) minutes post-end transfusion.

^k Serum or urine pregnancy test to be conducted only at the screening visit and prior to the first transfusion of Treatment Period 2. Not required if female subjects are not of child-bearing potential (ie, prior to menses onset, surgically sterilized, 1-year postmenopausal).

^l Record history of all RBC antibodies detected prior to first study transfusion; record only new antibodies thereafter, if applicable.

^m Test with Mirasol-treated RBCs if the previous study transfusion was a MIR RBC product. A segment from the prior MIR RBC unit should be used to conduct this test.

ⁿ Collect and hold blood sample for central RBC antibody testing when the antibody screen and crossmatch performed at the local lab either is positive for an antibody specific to MIR-treated RBCs or inconclusive. Samples will be sent to the central laboratory when the crossmatch to MIR RBCs and antibody identification at the Local Laboratory confirms the presence (or suspected presence) of an antibody specific to Mirasol-treated RBCs, or when the results are inconclusive (eg, positive crossmatch but unidentifiable antibody).

^o Samples for HLA antibody testing will be collected from all subjects prior to each transfusion in Period 1 only and sent to a central laboratory. The samples will be collected at the Early Termination visit if subject terminated early from the study during Period 1.

^p Visits on 1 Day Post Transfusion and 7 Days Post Transfusion may be conducted in the clinic or may utilize a remote nursing visit.

15 STUDY AND/OR TREATMENT DISCONTINUATION

All subjects are free to withdraw from study participation at any time and for any reason, specified or unspecified, and without prejudice. Similarly, an Investigator may discontinue any subject from study participation for any reason. The reason for the study discontinuation will be recorded in the eCRF.

15.1 Early Discontinuation/Study Termination

Reasons for a subject's withdraw from study participation or termination of the study by the Sponsor may include, but are not limited to the following:

1. Study completion as per protocol
2. Development of an AE that interferes with the subject's continued participation
3. Subject refuses further treatment and/or follow-up and withdraws consent
4. Investigator decision
5. Sponsor decision
6. Subject is lost to follow-up
7. Subject death
8. Development of an antibody with confirmed specificity to Mirasol-treated RBCs

16 LABORATORY TESTS

16.1 RBC Product Laboratory Testing

The following tests will be performed on the RBC products (MIR RBCs and REF RBCs) prior to transfusion for in vitro and in vivo correlation.

16.1.1 Local Laboratory

CBC: WBC count, RBC count, Hb concentration, and hematocrit.

16.1.2 Central Laboratory

Testing will be conducted for supernatant potassium, supernatant sodium, and supernatant hemoglobin (for calculation of percent hemolysis). Samples will be processed, stored, and shipped according to the instructions specified in the Manual of Procedures (MOP).

The percent hemolysis will be derived from the supernatant hemoglobin and CBC results, using the following formula:

$$\% \text{ Hemolysis} = [(\text{plasma free Hb}) * (1 - \text{Hct}) / \text{total Hb}] * 100$$

16.2 Clinical (Subjects) Laboratory Testing

16.2.1 Local Laboratory Tests

The following laboratory tests on subject blood samples will be performed locally. Copies of the current laboratory certifications and normal ranges will be provided to the Sponsor or designee prior to initiation of the study and upon every renewal throughout study conduct.

Pregnancy testing: Serum or urine pregnancy at Screening and prior to the first transfusion of Treatment Period 2. Not required if female subjects are not of child-bearing potential (ie, prior to menses onset, surgically sterilized, 1-year postmenopausal).

CBC: WBC count, RBC count, Hb concentration, hematocrit, and platelet count.

Haptoglobin: At the same time points when blood samples are collected for CBC analysis, samples will also be analyzed for haptoglobin concentration.

Plasma free hemoglobin: Prior to each transfusion, at 15 (± 5) min post-transfusion, and on Day 1 after each transfusion.

Chemistry: bilirubin, lactate dehydrogenase (LDH), alkaline phosphatase, aspartate aminotransferase (AST), alanine aminotransferase (ALT), potassium, sodium, blood urea nitrogen (BUN), creatinine, and ferritin.

Routine blood typing and crossmatch: Prior to each transfusion according to site standard procedures.

RBC antibody screen and identification: Local laboratories will conduct antibody screen prior to transfusions, on Day 7 (± 1 day) after each transfusion, at the End of Study Treatment Follow-up Visit, and at the Final Study Follow-up Visit according to site standard procedures. If the screen is positive, local laboratories will conduct RBC antibody identification.

If the identification is positive for MIR RBCs (or suspected positive) or is inconclusive, a sample will be sent to the central laboratory for further testing.

Crossmatch to MIR RBCs: This will occur at Day 7 (± 1 day), prior to the next transfusion, and at the End of Study Treatment Follow-up Visit whenever the previous study transfusion was a MIR RBC product per the randomized treatment allocation. A segment from the prior MIR RBC unit should be used to conduct this test.

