9 SAFETY ENDPOINTS

1. Incidence of treatment-emergent antibody with confirmed specificity to RBCs derived from Mirasol-treated WB.
2. Human leukocyte antigen (HLA) alloimmunization rates.
3. Treatment emergent adverse events.
4. Transfusion-related adverse events.
5. Serious adverse events.

6. Unanticipated adverse device effects.

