14.3.1 Prior to Each Transfusion Episode

Blood Product Procedures

1. Collect specimen from each unit prior to the transfusion (Section 16.1)
 - a. Local: Complete Blood Count (CBC)
 - b. Central: supernatant potassium, supernatant sodium, and supernatant hemoglobin

Subject Procedures

1. Measure weight
2. Conduct physical examination (only prior to the first transfusion of Treatment Period 2)

- a. Perform an abbreviated physical examination, including examination of general appearance, eyes/ears/nose/throat, pulmonary/chest, cardiovascular, abdominal, and neurological
3. Record vital signs within 1 hour prior to transfusion. Vital signs include HR, BP, RR, SpO₂, and temperature
4. Local Laboratory Tests (may be collected/tested at any time within 5 days before the transfusion unless otherwise noted)
 - a. Prior to Treatment Period 2 only: Serum or urine pregnancy test; not required if female subjects are not of child-bearing potential (ie, prior to menses onset, surgically sterilized, 1-year postmenopausal)
 - b. Routine blood typing and crossmatch per site standard practice
 - c. RBC antibody screen
 - o If positive, conduct RBC antibody identification and record only new RBC antibodies, if applicable
 - d. Crossmatch with RBCs derived from Mirasol-treated WB if the previous study transfusion was a MIR RBC product
 - e. CBC, plasma free hemoglobin; and haptoglobin within 1 hour prior to transfusion (Section 16.2.1)
 - f. Chemistry within 1 hour prior to transfusion (Section 16.2.1)
5. Collect blood from subject for Central Laboratory Tests (Section 16.2.2)
 - a. Collect and hold blood sample for RBC antibody testing, when the antibody screen and crossmatch performed at the local lab either is positive for an antibody specific to MIR-treated RBCs or inconclusive. See Section 16.2.2.1 for details regarding criteria for sending samples to the central laboratory
 - b. Collect blood sample for HLA testing, only during Treatment Period 1 (Section 16.2.2.2)
6. Record all concomitant medications taken starting from the day of the first study transfusion and throughout the study, including all blood products transfused (eg, off-protocol RBCs, platelets) (Section 17)
7. Record AEs, SAEs, and UADEs (Section 19). All AEs will be recorded from the time of the first study transfusion through the final follow-up or early termination visit

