16.2.2.1 RBC Antibody Testing

Samples will be collected from subjects prior to each study transfusion, at 7 days (\pm 1 day) after each transfusion, at the End of Study Treatment Follow-up Visit, and at the Final Study Follow-up Visit, and held pending antibody screen and identification results from the Local Laboratory. Samples that meet the requirements for shipment to the designated Central Laboratory as noted below will be processed, stored, and shipped according to the instructions specified in the MOP. Samples that do not meet these requirements will be destroyed after study completion according to the Hospital Site's standard procedures.

Requirements for sample shipment: This will be conducted when the crossmatch to MIR RBCs and antibody identification at the Local Laboratory confirms the presence (or suspected presence) of an antibody specific to MIR RBCs, or when the results are inconclusive (eg, positive crossmatch but unidentifiable antibody).

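### Protocol 16.2.1 and 16.2.2.1 give different triggers for central testing of Mirasol-specific antibody, and neither clearly routes a negative screen with a positive Mirasol crossmatch

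*Protocol*

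**What the plan says.** Protocol Section 9 lists as its first safety endpoint "Incidence of treatment-emergent antibody with confirmed specificity to RBCs derived from Mirasol-treated WB". SAP Section IX.F reports the number and percentage of such subjects. Neither document states which test result makes specificity confirmed.

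The route to the central laboratory is described in several places:

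- **Protocol 16.2.1.** The antibody screen follows site standard procedures. "If the screen is positive, local laboratories will conduct RBC antibody identification". Then: "If the identification is positive for MIR RBCs (or suspected positive) or is inconclusive, a sample will be sent to the central laboratory". The Mirasol crossmatch has its own paragraph ("A segment from the prior MIR RBC unit should be used to conduct this test"), with no action stated for a positive result.
- **Protocol 16.2.2.1, repeated in Table 14-1 footnote n.** The rule has two limbs. The first ships a sample "when the crossmatch to MIR RBCs and antibody identification at the Local Laboratory confirms the presence (or suspected presence) of an antibody"; what is meant is an antibody directed at Mirasol-treated cells. The second limb, an alternative to the first, ships a sample "when the results are inconclusive (eg, positive crossmatch but unidentifiable antibody". Samples are held until the local screen and identification results are known; the crossmatch is not named. Samples that do not qualify are destroyed once the study is over.
- **Collection.** 16.2.2.1 reads as unconditional: "Samples will be collected from subjects prior to each study transfusion, at 7 days" after each transfusion, and at both follow-up visits. Section 14.3.1 reads as conditional: "Collect and hold blood sample for RBC antibody testing, when the antibody screen and crossmatch performed at the local lab either is positive" for a MIR-specific antibody or is inconclusive. Section 14.3.4 and footnote n say the same.
- **Cross-references.** Sections 14.3.1, 14.3.4, 14.4 and 14.5 all refer the site to 16.2.2.1 for the sending criteria.

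**The concern.** The endpoint concerns an antibody against cells altered by the device. The only local test that the protocol says is run on Mirasol-treated cells is the crossmatch with a segment of the earlier MIR unit. If the routine screen uses ordinary reagent cells, an antibody directed solely at treated cells should give a negative screen and a positive Mirasol crossmatch. That result matters most for this endpoint, yet no section says in terms what to do with it.

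Two things are at stake. Sites relying on different sections could treat the same laboratory result differently, so the endpoint would not be ascertained uniformly. The likely direction of error for the device-specific pattern is also toward under-counting, and destroying unshipped samples rules out correction after the study ends. The undefined term *confirmed* also appears in Section 15.1, among the possible reasons for discontinuation, so the ambiguity is not confined to a table.

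**Working it through.** The documents give no figure to reproduce. The check sets each combination of local results against each shipment rule. Identification is run only after a positive screen (14.3.1, 14.3.4, 14.4, 14.5, 16.2.1), so a negative screen always means that identification was not done.

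Section 16.2.2.1 can be read in two ways:

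- **Narrow:** a positive crossmatch is always needed, together with an identification that was actually run and was MIR-specific, suspected or inconclusive.
- **Broad:** any inconclusive identification qualifies, and so does a positive crossmatch on which identification was never run.

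| Screen | Mirasol crossmatch | Identification | 16.2.1 | 16.2.2.1 narrow | 16.2.2.1 broad |
|---|---|---|---|---|---|
| neg | neg | not done | no | no | no |
| neg | pos | not done | **no** | **no** | **sent** |
| pos | neg | ordinary alloantibody | no | no | no |
| pos | neg | MIR-specific or suspected | **sent** | **no** | **no** |
| pos | neg | inconclusive | **sent** | **no** | **sent** |
| pos | pos | ordinary alloantibody | no | no | no |
| pos | pos | MIR-specific or suspected | sent | sent | sent |
| pos | pos | inconclusive | sent | sent | sent |

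Three of the eight patterns conflict or may conflict:

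1. **Negative screen, positive crossmatch.** 16.2.1 offers no route. 16.2.2.1 ships only on the broad reading, which depends on whether *unidentifiable* includes an antibody on which identification was never attempted. On the narrow reading the two sections agree, but only because both miss the case.
2. **MIR-specific identification, negative crossmatch.** 16.2.1 ships. The first limb of 16.2.2.1 does not, because it joins crossmatch and identification. It would ship only if the discordance itself were called inconclusive.
3. **Inconclusive identification, negative crossmatch.** 16.2.1 ships. 16.2.2.1 ships only if an inconclusive result does not need a positive crossmatch.

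Neither column for 16.2.2.1 matches 16.2.1: the narrow reading departs from it in patterns 2 and 3, the broad reading in patterns 1 and 2.

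**Holding rule.** 16.2.2.1 holds the sample pending screen and identification. In pattern 1 the screen is negative and identification is not run, so nothing in that sentence keeps the sample waiting for the crossmatch.

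**Final Study Follow-up.** Section 14.5 schedules a screen, identification if the screen is positive, and a held central sample. Neither 14.5 nor 16.2.1 schedules a Mirasol crossmatch there, so the joint limb of 16.2.2.1 cannot be met from that visit's tests.

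**Size.** An under-count would need the true antibody rate and the share of cases in pattern 1. The documents give neither. For scale only, one subject among the roughly 97 to be randomized is 1/97 = 1.0 percentage point of incidence. That describes the granularity of the endpoint and does not estimate the loss.

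**The case against.** The best defence is that 16.2.2.1 governs. Every visit section refers to it for sending criteria, footnote n repeats it, and none refers to 16.2.1. Section 16.2.1 says that a sample is sent if identification is positive; it does not say only if. An identification positive for MIR RBCs also makes little sense unless the crossmatch informs it. On an ordinary reading, a positive crossmatch that the routine screen does not explain fits the inconclusive example. Conditional collection may be loose phrasing, since Table 14-1 marks the central sample at the same visits. The Manual of Procedures, which is not available here, may settle the matter. Finally, the protocol reports no evidence of neoantigenicity in IMPROVE II, so cases may be rare.

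Much of this stands, and it rules out two stronger readings that a reader might infer:

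- **That a screen-negative, crossmatch-positive sample is never sent.** This describes 16.2.1 in isolation. The section that the visits cite can be read to cover the case.
- **That such a subject cannot count as an event.** This assumes that confirmation must be central. Neither document says so: 16.2.1 sends samples for further testing, and 16.2.2.1 uses the verb *confirms* for the local laboratory's own crossmatch and identification.

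Nor do the documents make central confirmation a precondition for discontinuation; the list in 15.1 is open-ended and includes investigator decision.

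The defence does not remove the narrower problem. Being the cited section does not make 16.2.2.1 clear on an antibody that was never put through identification. It leaves the reverse discordance in conflict with 16.2.1, and it omits the crossmatch from the holding rule. If confirmation is local, 16.2.2.1 ties it to identification, which a negative screen does not trigger.

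**Conclusion.** The point holds as an inconsistency that should be corrected. The shipment triggers differ between 16.2.1 and 16.2.2.1 with footnote n. A negative screen with a positive Mirasol crossmatch is not clearly routed anywhere, the collection instructions read differently, and *confirmed* has no operational definition. Sites could therefore handle the same result differently, and the incidence of the first-listed safety endpoint may be under-counted. The amount cannot be computed from the documents.

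This rests on two assumptions. The first is that the site-standard screen does not use Mirasol-treated cells; the documents describe it only as site standard. The second is that the Manual of Procedures does not already give a single rule. If it does, the protocol text still needs to match it. The primary efficacy analysis is not affected.

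**What to change.** Reconcile 14.3.1, 14.3.4, 14.4, 14.5, 16.2.1, 16.2.2.1 and Table 14-1 footnote n into one rule, and align the Manual of Procedures with it:

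- Collect and hold a sample at every listed visit, pending the screen, identification and Mirasol crossmatch results.
- Ship it whenever the Mirasol crossmatch is positive and not explained by an identified ordinary alloantibody, whatever the screen shows.
- Ship it also whenever identification is positive, suspected or inconclusive for MIR RBCs, whatever the crossmatch shows.
- State the shipment trigger for the Final Study Follow-up, where no Mirasol crossmatch is scheduled.
- In SAP Section IX.F, state which result, local or central, makes specificity confirmed.

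The cost is protocol, manual and SAP wording. The crossmatch, the held sample and the central test are already planned, so the only operational burden is a few more shipped samples.
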